Adverse events (AEs) and concomitant medication use will be collected at each 6-month visit to the clinical unit. Blood draws for clinical safety laboratory tests and abbreviated physical examinations (including weight and vital signs) will also be performed at each 6-month clinic visit. ECGs will be performed every 12 months on an annual basis. A telephone call will be made at 3-month intervals between clinic visits to assess safety and use of concomitant medications.

For the evaluation of efficacy, the Patient Global Assessment, NYHA classification, KCCQ, 6-minute walk test, and efficacy-related clinical laboratory tests (serum levels of troponin T, troponin I, and NT-pro-BNP) will be determined every 6 months. In addition, echocardiograms will be performed every 12 months on an annual basis.

An end of study visit including all safety and efficacy assessments will occur upon subject completion of the study, premature withdrawal (for any reason), or in the event of program discontinuation by the Sponsor.

Statistical Methods:

Safety and efficacy data will be summarized using descriptive statistics. For continuous variables, the means, standard deviations, medians, and ranges will be presented; for categorical variables, counts and percentages (with 95% confidence intervals) will be presented. Safety and efficacy data will also be shown in individual subject listings.

The cumulative efficacy data (starting from Protocol Fx1B-201) as measured by the Patient Global Assessment, NYHA classification, KCCQ, 6-minute walk test, echocardiograms, and serum levels of troponin I, troponin T, and NT-pro-BNP will be presented.

The endpoints of mortality and hospitalization (all cause and cardiac-related) will be analyzed individually and as composite measures. A Kaplan-Meier plot of time to event from the baseline of Protocol Fx1B-201 will be generated, and the event rate and associated 95% confidence intervals will be presented at 1, 2, 3, and 4 year intervals since the start of the investigational drug. The baseline data from protocol Fx1B-201 will be used as baseline for the analyses. Interim analyses will be performed during the course of the study to allow for the reporting of safety and efficacy data from the ongoing study.

SCHEDULE OF ACTIVITIES

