9. DATA ANALYSIS/STATISTICAL METHODS

Detailed methodology for summary and statistical analyses of the data collected in this study will be documented in a Statistical Analysis Plan, which will be maintained by the sponsor. This document may modify the plans outlined in the protocol; however, any major modifications of the primary endpoint definition and/or its analysis will also be reflected in a protocol amendment.

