9.2.8. Mortality and Hospitalization

The endpoints of mortality and hospitalization (all cause and cardiac-related) will be analyzed individually and as composite measures.

A Kaplan-Meier plot of time to event from the start of Protocol Fx1B-201 will be generated, and the event rate and associated 95% confidence intervals will be presented at 1, 2, 3, and 4 years since the start of the investigational drug.

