## 1. AMENDMENTS FROM PREVIOUS VERSION(S)

Amendment 1, 31Oct2015: The Statistical Analysis Plan has been amended to include the following:

Change	Date	Section(s) Affected	Corresponds to a Protocol Amendment	Statistician
1. Changed the word patient to subject in order to agree with the amended protocol.	May 29, 2014	Throughout	Yes (# 1)	PPD
2. Additional information on the use of interim analyses.	May 29, 2014	3.2	Yes (# 1)	PPD
3. Additional clarification of visit windowing	May 29, 2014	Appendix 2	No	PPD
4. Additional clarification of missing data rules is included.	May 29, 2014	Appendix 3	No	PPD
5. Clarification of the categorical outcome variable analyses has been included, as well as the addition of shift tables for the analysis of these variables.	May 29, 2014	8.1.2	No	PPD
6. The list of the laboratory measures to be summarized was shortened to those laboratory measures which are potentially related to disease. All values will be listed in the subject listings. Additionally, duplicated laboratory measures were removed.	May 29, 2014	6.2 item 7	No	PPD
7. The report of physical examinations has been changed from a summary to a listing and a listing of medical history has been added	May 29, 2014	6.3	No	PPD

8. The LOCF analysis has been removed, due to the nature of the discontinuation criteria from this study LOCF is not an appropriate analysis.	May 29, 2014	7	No	PPD
9. The specification and summary of the use of pacemakers and/or defibrillators were added.	May 29, 2014, Nov 3, 2015	8.3	No	PPD
10. The cox regression models for time to event were removed due to the single arm study design.	May 29, 2014	8.1.3	No	PPD
11. Time to event analysis has been modified to specify time from randomization and time from onset of disease.	May 29, 2014	8.1.3	No	PPD
12. Added specifications for a table of clinically significant ECGs.	May 29, 2014	8.3	No	PPD
13. Added formulae for calculating QTc correction factors (QT cB and QT cF ).	May 29, 2014	Appendix 1.3	No	PPD
14. Replaced the scoring for the KCCQ with a clearer version of the manual to agree with the programming used in Fx1B-201.	May 29, 2014	Appendix 1.1	No	PPD
15. Clarified Section 6.1 and 8.2 for efficacy endpoints and analyses to be consistent with the protocol.	May 29, 2014	6.1 and 8.2	No	PPD

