## 8.3. Safety Analyses

Safety data will be summarized for the safety analysis population.

**Treatment and Disposition of Subjects:** Subject evaluation groups will show end of study subject disposition and will show which subjects were analyzed for efficacy, as well as for

safety (adverse events and laboratory data). Frequency counts will be supplied for subject discontinuation(s) by treatment.

A listing of treatment duration for each subject will be reported in accordance with the sponsor reporting standards.

**Demographic and Baseline Characteristics.** A break-down of demographic data will be provided for age, race, weight, body mass index, and height. Each will be summarized by sex at birth and ‘All Subjects’ in accordance with the sponsor reporting standards. All baseline and disease characteristics will also be summarized for Fx1B-201 and B3461026, respectively.

**Discontinuations.** Subject discontinuations or temporary discontinuations due to adverse events will be detailed and summarized.

**Adverse events (AEs):** Adverse events will be summarized by causality and severity.

**Mortality and Hospitalization (all-cause and cardiac-related):** Time to all-cause mortality and time to cardiac-related mortality will be calculated from the first dose of the randomized treatment in Study Fx1B-201, and from onset of symptom, respectively. For cardiac-related mortality, subjects who died for reasons other than cardiovascular will be designated as censored at the time of death. Subjects alive at the end of the study will be censored at the last visit date. Death after discontinuation will be censored at time of discontinuation. For subjects who have received a liver and/or heart transplant, time will be censored at the time of transplant. The analyses will use the methods described for time to event endpoints in [Section 8.1.3](#). The analyses will be performed on the safety analysis population (defined in [Section 5.1](#)).

The number and percentage of subjects hospitalized (all-cause and cardiac-related) during the study will be summarized descriptively.

**Hematology, Biochemistry and Urinalysis:** Descriptive statistics will be provided for each test result and for change from baseline by visit.

Baseline is defined as the last evaluation prior to the first dose of study drug in Study Fx1B-201.

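### The SAP defines no death/hospitalization composite, which protocol 9.2.8 names, and reports hospitalization as a percentage tied to no fixed time

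*SAP*

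**What the plan says.** **Protocol.** Section 2.2 lists mortality and hospitalization among the efficacy endpoints. Section 9.2.8 states: "The endpoints of mortality and hospitalization (all cause and cardiac-related) will be analyzed individually and as composite measures". It then sets the display: "A Kaplan-Meier plot of time to event from the start of Protocol Fx1B-201 will be generated". Yearly rates with 95% intervals are to accompany it for years 1 to 4 of drug. The synopsis repeats the composite and the plot, with a slightly different origin: "A Kaplan-Meier plot of time to event from the baseline of Protocol Fx1B-201 will be generated". Section 9 says of the SAP: "This document may modify the plans outlined in the protocol".

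**SAP.** Section 6.2, item 8, defines all-cause and cardiac-related mortality, and all-cause and cardiac-related hospitalization, each on its own. Section 8.3 then sets the clock for deaths: "Time to all-cause mortality and time to cardiac-related mortality will be calculated from the first dose of the randomized treatment in Study Fx1B-201", with a second clock from symptom onset. It adds censoring rules for deaths, points to section 8.1.3 and names the safety population. Hospitalization gets one separate sentence: "The number and percentage of subjects hospitalized (all-cause and cardiac-related) during the study will be summarized descriptively". No composite is defined in sections 6, 7 or 8, and section 8.2 leaves mortality and hospitalization out of the efficacy analyses.

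**The concern.** A programmer who follows the SAP as written would produce mortality curves and a hospitalization count, but no composite. That leaves out a named efficacy outcome, one that protocol 1.2.4 reports at 12 months for both the parent study and TRACS.

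The hospitalization percentage is also hard to interpret. A subject followed for one year and a subject followed for nine count equally in the denominator. Death ends the chance of a later admission, so higher mortality can make the percentage look better. The SAP does not say whether admissions during Fx1B-201 count, although the protocol's clock starts there.

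**Working it through.** **1. Does generic SAP text supply the missing analysis?**

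- Section 8.1.3 applies Kaplan-Meier to every time-to-event endpoint, but no section makes hospitalization or a composite such an endpoint.
- In section 8.3 the pointer to 8.1.3 closes the mortality rules and comes before the hospitalization sentence.
- Section 7 says to use the first occurrence of an event, but names no endpoint.
- Sections 4.2 and 8.1.2 add a 95% interval (exact, under 8.1.2) to the hospitalization percentage. That covers sampling error, not unequal follow-up.

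So the generic text does not supply it.

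**2. Composite against hospitalization alone.** Inputs are the 12-month counts in protocol 1.2.4 (cardiovascular hospitalization). The stated percentages reproduce as x/n:

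| | Death | Hospitalized | Composite |
|---|---|---|---|
| Fx1B-201 | 2/35 = 5.7% | 9/35 = 25.7% | 9/35 = 25.7% |
| TRACS | 6/29 = 20.7% | 10/29 = 34.5% | 13/29 = 44.8% |

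Died without an admission = composite − hospitalized. Exact (Clopper-Pearson) 95% limits are the 0.025 quantile of Beta(x, n−x+1) and the 0.975 quantile of Beta(x+1, n−x), with a lower limit of 0 when x = 0.

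- TRACS: 13 − 10 = 3, and 3/29 = 10.3 points (2.2 to 27.4).
- Fx1B-201: 9 − 9 = 0, and 0/35 = 0 points (0 to 10.0).

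**3. How far a crude percentage depends on follow-up (illustration only).** Assume constant, independent hazards h = −ln(1−p) from the Fx1B-201 proportions: hospitalization a = −ln(26/35) = 0.297 per year, death b = −ln(33/35) = 0.059 per year. The expected percentage hospitalized by time T is a/(a+b) × [1 − exp(−(a+b)T)], averaged over an assumed follow-up distribution:

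- uniform over 0 to 2 years: 23.8%
- uniform over 0 to 4 years: 39.0%
- uniform over 0 to 10 years: 60.7%
- 10 years potential follow-up for everyone: 81.1%

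The hospitalization hazard is the same in every line. With 10 years potential follow-up, raising 12-month mortality from 5.7% to 20.7% lowers the percentage from 81.1% to 55.9%, again with that hazard unchanged.

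The model is rough. It gives a 12-month composite of 30.0% against the observed 25.7%, because in Fx1B-201 both deaths fell among hospitalized subjects. It shows the direction and scale of the dependence and predicts nothing.

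**4. Why the population must be stated.** In Fx1B-201, 2 + 9 − 9 = 2, so both deaths were in hospitalized subjects. That leaves 9 − 2 = 7 hospitalized among 35 − 2 = 33 survivors. The SAP safety population is limited to Fx1B-303 enrollees. If all 33 survivors enrolled (an assumption; the documents give no enrolment count), the year-1 composite on the Fx1B-201 clock would be 7/33 = 21.2%, which is 4.5 points below 9/35 = 25.7%, with 0/33 deaths instead of 2/35.

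**The case against.** **Silence is not deletion.** No SAP sentence cancels protocol 9.2.8, and section 9 lets the SAP modify the plan. This stands against any claim of a protocol breach, which a reader might infer. The proviso in section 9 that major changes need an amendment concerns the primary endpoint, and section 9.2.1, under that heading, does not list mortality or hospitalization. It does not cure the gap, since section 9 also leaves the detailed methods to the SAP.

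**The change log proves little.** A reader might infer an unexplained removal, because the log gives reasons for other deletions, for example "The cox regression models for time to event were removed due to the single arm study design". The log records changes from one SAP version to the next. Nothing shows that a composite was ever in a SAP, so its absence from the log says nothing about intent.

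**Kaplan-Meier for hospitalization alone is not expressly required.** Protocol 9.2.8 does not say which events the plot covers. Reading it to include hospitalization is natural, but the firm commitment is the composite.

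**The practical effect may be small.** The study has no control group and no hypotheses, expects up to 35 subjects, and plans individual listings, including each subject's treatment duration. Neither document plans a comparison of Fx1B-303 hospitalization with TRACS. In the only treated cohort the composite added nothing, and TRACS had a different genotype mix (11/29 V122I against 4/35). All of this stands. It limits the weight of the point without supplying the missing definition.

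**Conclusion.** The point holds as an omission that should be repaired. The protocol names composites; the SAP defines none, limits its time-to-event rules to death, and gives hospitalization as a percentage with an exact interval but no time point. The observed difference between composite and hospitalization at 12 months ranges from 0 points (parent study; interval up to 10.0) to 10.3 points (TRACS; 2.2 to 27.4). These counts are of cardiovascular admissions. All-cause admissions, or the SAP's MedDRA-based cardiac definition, could give other figures. The dependence on follow-up rests on the collection rules; its illustrated size rests on assumed constant hazards.

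The documents do not support reading this as a breach, as proof of deliberate removal, or as a threat to any test. The cost is a less complete and less interpretable report.

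**What to change.** In SAP 8.3:

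- Add time to first death or all-cause hospitalization, and time to first death or cardiac-related hospitalization, by Kaplan-Meier with yearly rates and 95% confidence intervals. The protocol does not define the components; all-cause death is suggested in both because that is closest to the composite in protocol 1.2.4.
- Use the Fx1B-201 origin that protocol 9.2.8 sets. The first Fx1B-201 dose, already used for mortality, would serve.
- State which recorded date defines a hospitalization, and the censoring rules for withdrawal, transplant and move to prescription supply.
- State the analysis population and whether Fx1B-201 events count. If only Fx1B-303 enrollees are included, label the year-1 estimates as conditional on completing Fx1B-201.
- Keep the number and percentage hospitalized as a supplement. Cumulative incidence of hospitalization alone, with death as a competing event, is optional.
- If the composite is dropped on purpose, say so and give the reason.

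The cost is SAP wording and a few extra tables. SAP 6.2 already identifies hospitalizations from the adverse event form, and SAP 8.1.3 already provides yearly intervals.

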Baseline electrocardiogram and 24-hour Holter monitoring demonstrated substantial conduction and rhythm abnormalities, including bundle branch blocks and atrial fibrillation/flutter. There were no clinically relevant changes over time in these assessments, with perhaps slight improvement in cardiac autonomic function as demonstrated by improved heart rate variability indices.

Over the 12 months of tafamidis treatment, the patients' quality of life was maintained as was their functional status, as assessed by the SF-36, and KCCQ and PGA, respectively. The majority of these results were also better when compared with TRACS.

Seven patients participated in both TRACS (median follow up 12.5 months, with range of 6-26 months) and in Study Fx1B-201. All seven patients completed 12 months of treatment with tafamidis. However, given the small number of patients, it is difficult to assess whether disease progression was different during treatment with tafamidis as compared to standard of care in TRACS. The rate of cardiovascular hospitalization was similar between the two 12-month periods, with some evidence of stabilized cardiac function (ejection fraction and fractional shortening) observed following treatment with tafamidis.

Overall, tafamidis was effective in achieving and maintaining TTR stabilization in both wild-type and V122I patients and showed an apparent stabilization of the progression of cardiac disease.

The safety data described reflect exposure of 127 TTR-FAP patients to 20 mg of tafamidis administered daily for an average of 538 days (ranging from 15 to 994 days). The population was composed of adult patients diagnosed with symptomatic TTR-FAP, with a mean age of approximately 44 years; approximately half of the patients were female, and approximately 90% of the patients were Caucasian. Note that primary evidence of safety and efficacy was obtained from a placebo-controlled 18-month study in patients with TTR-FAP.

Table 1 provides a summary of the most common treatment emergent adverse events (TEAEs) ($\geq 5\%$ in tafamidis treatment group) during study Study Fx-005.

Table 1. Summary of Most Common ($\geq 5\%$ in Tafamidis Treatment Group) Treatment-Emergent Adverse Events Sorted in Descending Incidence in the Overall Tafamidis Group – TTR-FAP Patients, Study Fx-005 (Safety Population)

MedDRA Preferred Term	Number (%) of Subjects	
	Tafamidis 20 mg N=65	Placebo N=63
Number of patients with at least 1 AE	60 (92.3)	61 (96.8)

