## 6.2. Safety Endpoints

- 1. Echocardiography: at each visit and change from baseline
  - a. Interventricular septal thickness (mm)
  - b. Posterior left ventricular wall thickness (mm)
  - c. Left atrial diameter (mm)
  - d. Left atrial volume (cc)
  - e. Left ventricular end diastolic diameter (mm)
  - f. Left ventricular mass (g)
  - g. Ejection fraction (%)
  - h. Right ventricular wall thickness (mm)
- 2. Doppler data
  - a. E/A ratio
  - b. Mitral Deceleration time (msec)
- 3. Tissue Doppler
  - a. Septal s', e', a' (cm/sec)
  - b. Lateral s', e', a' (cm/sec)
  - c. Pericardial effusion (yes/no)
  - d. Valvular abnormalities (thickening, regurgitation)
- 4. Calculated Echo variables will include, but are not limited to:
  - a. Relative LV wall thickness (Post wall thickness X 2 divided by LVED)
  - b. LA Volume index (LA size/body surface area)
  - c. LV mass/voltage ratio (LV mass divided by largest voltage on ECG)
  - d. e:e' ratio
- 5. Select echocardiogram parameters will be categorized as indicated below:
  - a. Left ventricular posterior wall thickness  $\geq$  13 mm
  - b. Left ventricular septal thickness  $\geq$  13 mm

- c. Right ventricular thickness  $\geq$  7 mm
- d. E/A ratio  $\geq$  2
- e. E/Eprime Lateral  $>$  15
- f. E/Eprime Septal  $>$  15
- g. Ejection fraction  $<$  50%
- h. E deceleration time  $\leq$  150 msec
- i. Isovolumic relaxation time (IVRT)  $\leq$  70 msec
- j. Any valve thickening
- k. Abnormal respiratory variation of inferior vena cava
- l. Pericardial effusion

6. ECG values: at each visit and change from baseline

- a. PR interval (msec)
- b. RR interval (msec)
- c. QRS interval (msec)
- d. QT and QTc interval (msec)
- e. heart rate (bpm)
- f. overall interpretation, normal/ abnormal findings and clinical significance
- g. Corrected QTc will be calculated using Bazett's and Fridericia's correction formulas.
- h. QTc  $>$  450 msec
- i. QTc  $>$  480 msec
- j. QTc  $>$  500 msec
- k. Change in QTc between 30 msec (inclusive) and  $<$  60 msec
- l. Change in QTc  $\geq$  60 msec
- m. Change in QTc  $\geq$  90 msec

7. Clinical laboratory tests: at each visit and change from baseline

The following list of clinical laboratory endpoints was collected during the course of the study. However, the summary tables will be restricted to the measures indicated with an asterisk (\*). All measures will be included in the subject listings.

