**Cardiac Measures:** Changes from baseline (defined as the last evaluation prior to the first dose of study drug) will be summarized for each of the cardiac parameters listed above by visit. Clinically significant changes in ECG measures (as indicated by the items in [Section 6.2, #6](#), item h through m) at any point during the study will be summarized.

Pacemaker and defibrillator insertion procedures will be identified through a programmatic search of potentially related terms in the clinical database coupled with a manual review by Pfizer Clinical.

The following MedDRA Lower Level Terms (codes) will be applied to the Medical History, Adverse Events, and Investigator Comments to identify potential procedures in the clinical

database: CARDIOVERTER PLACEMENT (10053015), INSERTION OF IMPLANTABLE CARDIOVERTER DEVICE (10052044), CARDIAC PACEMAKER INSERTION (10007598), PACEMAKER INSERTION (CARDIAC) (10033352), DEFIBRILLATOR/PACEMAKER INSERTION (10069072), IMPLANTABLE DEFIBRILLATOR INSERTION (10049442).

The following terms will also be searched to identify potential associated procedures collected in the Investigator Comments CRF: pacemaker, implantable cardiac device, ICD, AICD, cardioversion, cardioverter, defibrillator, ventricular fibrillation, ventricular tachycardia.

Final search criteria and categorization of pacemaker and defibrillator will be based on the results of the clinical review and will be described in the programming plan prior to database finalization.

The number and percentage of subjects with pacemaker or defibrillator insertion procedures (defined above) will be summarized by category and for overall at baseline of Fx1B-201, the number and percentage of subjects who have such devices implanted during the course of Fx1B-201 and during the course of B3461026 (Fx1B-303), respectively.

**Vital signs:** Will be summarized using descriptive statistics, to include: values at each visit, change from baseline to each visit and a categorization of clinically significant changes.

Significant changes from baseline are defined as follows:

- Systolic Blood Pressure (mmHg) Decrease (Change  $\leq$  -20, or Value < 90)
- Systolic Blood Pressure (mmHg) Increase (Change  $\geq$  20, or Value > 180)
- Diastolic Blood Pressure (mmHg) Decrease (Change  $\leq$  -15, or Value < 50)
- Diastolic Blood Pressure (mmHg) Increase (Change  $\geq$  15, or Value > 105)
- Heart Rate (bpm) Decrease (Change  $\leq$  -15, or Value < 50)

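### The QTc outlier table does not separate ventricularly paced or wide-QRS ECGs, so enough QRS widening alone can count as a clinically significant QTc change

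*SAP*

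**What the plan says.** SAP 6.2, item 6, lists the ECG endpoints. Items h to j are absolute QTc values above 450, 480 and 500 msec. Item k is "Change in QTc between 30 msec (inclusive) and" less than 60 msec, item l is a rise of at least 60 msec, and item m a rise of at least 90 msec. SAP 8.3 (Cardiac Measures) presents this set as clinically significant ECG changes: "item h through m) at any point during the study will be summarized".

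On the correction, SAP 6.2 says "Corrected QTc will be calculated using Bazett's and Fridericia's correction formulas". Appendix 1.3 gives both formulas, and heart rate is the only adjustment in them.

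On the population, Protocol 1.2.4 reports that ECG and Holter recordings at the parent-study baseline "demonstrated substantial conduction and rhythm abnormalities, including bundle branch blocks and atrial fibrillation/flutter". SAP 8.3 also provides for devices: "The number and percentage of subjects with pacemaker or defibrillator insertion procedures (defined above) will be summarized by category". The count covers devices present at the Fx1B-201 baseline, "subjects who have such devices implanted during the course of Fx1B-201", and those implanted during the present study. One matter is left to the programming plan: "Final search criteria and categorization of pacemaker and defibrillator will be based on the results of the clinical review". That deferral concerns finding and classifying devices, not handling ECGs.

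Neither document has a rule that excludes, flags or separates ECGs with ventricular pacing, bundle branch block or wide QRS.

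**The concern.** QT runs from the start of QRS to the end of the T wave, so it contains QRS. If pacing or a new block widens QRS while repolarisation stays the same, QT lengthens by the amount of the widening. The rate correction then scales that lengthening; it does not remove it. The plan's rule, followed exactly, can therefore record a conduction change as QTc prolongation.

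Three features of the plan add to this. A flag at any one annual ECG, over up to 10 years, is enough. Change is measured from the pre-treatment Fx1B-201 baseline (SAP 8.1.1), so a block or device acquired in either study can contribute. There is no control group (Protocol 3.1) against which to set the background rate of conduction disease.

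Items h to j raise a separate difficulty. They are absolute values inside a set labelled as changes, so a subject with a wide QRS and a long QTc before treatment can be counted although nothing has changed.

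What is at stake is how the QTc outlier rows are read in a descriptive single-arm safety report.

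**Working it through.** The plan states no QTc event rate, so there is no figure to reproduce. The check applies the SAP's own formulas and cut-offs to an illustrative ECG.

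**Inputs from the documents.** QTcF = QT / RR^(1/3) and QTcB = QT / RR^(1/2), with RR = 60/HR (SAP Appendix 1.3). Cut-offs h to m are from SAP 6.2. Up to 35 subjects are expected (Protocol 9.1). Items h to m do not say which correction they use, so both are shown.

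**Assumptions not in the documents.** Heart rate is 60 to 80 bpm and the same at both ECGs. JT (QT minus QRS) is constant at 320 msec. Narrow QRS is 90 msec and widened QRS 120 to 180 msec.

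**Step 1: widening needed for a change category.** With JT and heart rate constant, change in QTc = (QRS widening) / RR^p, where p is 1/3 or 1/2. The widening needed is therefore cut-off × RR^p. At 80 bpm RR = 0.75, so by Bazett 30 × 0.75^(1/2) = 26.0 msec. This step does not depend on the JT value chosen.

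| HR (bpm) | Correction | Rise of 30 | Rise of 60 | Rise of 90 |
|---|---|---|---|---|
| 60 | both | 30.0 | 60.0 | 90.0 |
| 70 | Fridericia | 28.5 | 57.0 | 85.5 |
| 70 | Bazett | 27.8 | 55.5 | 83.3 |
| 80 | Fridericia | 27.3 | 54.5 | 81.8 |
| 80 | Bazett | 26.0 | 52.0 | 77.9 |

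**Step 2: which items are met, at 70 bpm.** The starting point is QRS 90, QT 320 + 90 = 410, QTcF 432 and QTcB 443, with no item met.

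| QRS | QT | QTcF (change) | QTcB (change) | Items met |
|---|---|---|---|---|
| 120 | 440 | 463 (+31.6) | 475 (+32.4) | h, k |
| 140 | 460 | 484 (+52.6) | 497 (+54.0) | h, i, k |
| 160 | 480 | 505 (+73.7) | 518 (+75.6) | h, i, j, l |
| 180 | 500 | 526 (+94.7) | 540 (+97.2) | h, i, j, l, m |

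The absolute items depend on the assumed JT and rate. At 80 bpm the narrow-QRS ECG already has QTcF 451 and QTcB 473, so item h is met before any widening.

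**Step 3: a stable wide QRS.** With QRS 160 msec at both baseline and follow-up and 70 bpm, QTcF is 505 both times. The change is 0, so none of k to m is met, yet h, i and j all are.

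**Step 4: a measure without QRS.** Rate-corrected JT by the Fridericia exponent is (410 − 90) / 0.950 = 337 msec before widening and (480 − 160) / 0.950 = 337 msec after. The change is 0, as it must be when JT is held constant.

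**Step 5: weight of one subject.** If n = 35, 1/35 = 2.9% (exact 95% interval 0.1% to 14.9%). For comparison, 3/35 = 8.6% (1.8% to 23.1%) and 5/35 = 14.3% (4.8% to 30.3%).

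**The case against.** The strongest reply is that the table does not stand alone. SAP 6.2 also reports PR, RR, QRS, heart rate, and overall interpretation with clinical significance. Adverse events and device insertions are summarised, the investigator reviews each ECG (Protocol 7.4), and individual listings are planned. With at most 35 subjects and annual ECGs, a careful reader could check each flagged subject. The study has no hypotheses (SAP 4.1), so no test, error rate or decision rule is affected. Protocol 1.2.3 reports no potential for QT prolongation, and Protocol 1.2.4 reports no clinically relevant ECG changes over the 12 months of the parent study.

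Much of this stands, and it limits the weight of the point. It does not supply the missing rule. Nothing in the plan uses QRS or the ECG interpretation to qualify the QTc rows, and 12 quiet months say little about up to 10 years. If a true drug effect is unlikely, that is more reason to show how much of the table reflects conduction.

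A reader might infer more than the documents support:

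- *That every implant or new block is counted.* It is not. The ECG must cross a cut-off, and widening below about 26 msec meets no change category at these rates. A device that is not pacing the ventricle on that tracing need not widen QRS, and a stable baseline block creates no flag under k to m.
- *That the table will mostly reflect conduction disease, or is the only electrical safety signal.* No rate of block or pacing is given, so no number of affected subjects can be estimated, and the other ECG and adverse event summaries exist.
- *That the "LV mass/voltage ratio (LV mass divided by largest voltage on ECG") is distorted in a known direction.* That item (SAP 6.2, 4c) lacks a paced-ECG rule too, but it cannot produce a QTc flag, and the documents show no direction of bias.

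**Conclusion.** The gap is real and modest. As written, SAP 8.3 can record QRS widening of about 26 to 30 msec or more as a clinically significant QTc rise, and can record a long-standing wide QRS under the absolute cut-offs with no change. The 26 to 30 msec range rests on 60 to 80 bpm, equal heart rate at both ECGs and unchanged repolarisation. The absolute-value examples also rest on the assumed JT of 320 msec. How many subjects this would affect is unknown; each adds 2.9 percentage points if n = 35. The consequence is confined to the interpretation of descriptive safety rows, but in a single-arm descriptive study those rows are part of what is delivered. The correction is cheap and should be made.

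**What to change.** In SAP 8.3:

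1. Keep the table of items h to m for all ECGs.
2. Add the same table restricted to ECGs without ventricular pacing and with QRS below a width fixed in advance. For items k to m, both the baseline and the follow-up ECG should qualify. Judge pacing from the interpretation of that ECG, and use device dates only as a prompt to check. Treating every ECG after an implant as paced would misclassify unpaced tracings.
3. For the remaining ECGs, keep the same outlier categories, so that these subjects do not lose QT monitoring. Add the change from baseline in rate-corrected JT or in a QRS-adjusted QTc, with the formula stated. Plain QT minus QRS would drop the rate correction.
4. For items h to j, show whether the cut-off was already met at baseline.
5. Flag paced and wide-QRS status in the listings.

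QRS, QT, heart rate, ECG interpretation and device insertions are already endpoints or already searched for. The cost is SAP wording, a per-ECG flag and one table split, with small numbers in each part. No information is lost, because the all-ECG table remains.
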